6. STUDY PROCEDURES

6.1. Study Visits

For each subject, the duration of the study, including the screening period and the follow-up visit will not exceed 7 months.

AEs and concomitant medication and treatment will be collected throughout the study and are not specified for each visit.

PE-arm: high dose IVIg will be given after the last session of PE. Since the number of sessions with PE may be different between subjects and thus not given at a specific visit and will not be described below. Samples for DSA and PD will be taken 24 hours after the last session of PE. A PD sample will be taken prior to and after (may be the day after) completion of high dose IVIg. If there are scheduled PD samples at these time points, no extra samples are needed. Rituximab will be given 5 days after completion of the IVIg infusion.

6.1.1. Visit 1 (screening)

Subjects will be informed about the study, the anticipated benefits and theoretical risks, in writing and verbally and sign the informed consent form.

The screening visit will include the following:

- Signing of informed consent form by subject
- Demographics (age, sex and race)
- Number of pregnancies (if applicable)
- Medical/surgical history, including transplantation and previous AMR(s)
- The 3 latest creatinine values prior to the current AMR will be collected. The latest value will be used as baseline value for inclusion
- Physical examination
- Height and weight
- Vital signs (blood pressure, pulse rate, respiratory frequency, and body temperature)
- PCR test for SARS-CoV-2 virus
- Pregnancy test (serum)
- ECG
- Safety laboratory tests ([Table 5](#))
- Urine sample for measurement of albumin/creatinine ratio
- DSA sample will be collected

- Kidney biopsy will be performed. Kidney biopsy performed within standard of care and 5 days prior to screening can be used for inclusion and does not need to be repeated at screening.
- Sample for ADA (IgE) (no need to wait for result before start of treatment)
- Check of inclusion and exclusion criteria
- Randomisation to treatment arm

6.1.2. Visit 2 (treatment), Day 1-5

The following activities and assessments will be performed on day 1, prior to start of treatment with imlifidase or PE:

- Blood pressure, pulse rate and respiratory frequency, and body temperature
- Baseline samples for DSA, PK, PD, and ADA (IgG) will be collected prior to start of treatment
- P-creatinine
- Urine sample for measurement of albumin/creatinine ratio

Imlifidase arm: Methylprednisolone, antihistamine and antibiotic prophylaxis will be administered before the imlifidase infusion.

PE arm: Methylprednisolone and antibiotic prophylaxis will be administered before the first treatment.

Treatment with antibiotics will continue until IgG levels return to acceptable values as judged by the investigator. Methylprednisolone will be administered according to treatment schedule, see [Section 5.3](#).

The following activities will be performed after the start of treatment:

- Blood pressure and pulse rate will be monitored at 2, 6, 24, 48, 72, and 96 hours
- Respiratory frequency and body temperature will be monitored at 24, 48, 72, and 96 hours
- Safety laboratory tests ([Table 5](#)) will be collected at 24, 48, 72, and 96 hours
- Urine sample for measurement of albumin/creatinine ratio at 24, 48, 72, and 96 hours.
- Imlifidase arm: Samples for PK will be collected at 30 minutes and 1 hour
- Samples for DSA, PK and PD will be collected at 2 and 6 hours
- Samples for DSA, PK, PD and ADA (IgG) will be collected 24 hours after treatment.
- Samples for DSA, PK and PD will be collected at 48, 72, and 96 hours. The 72-hour sample must be taken prior to high dose IVIg is given in the imlifidase arm

Imlifidase arm: High dose IVIg will be given on day 4 (at least 72 hours after the imlifidase infusion). Dose may be given over 2 days as judged by the investigator.

6.1.3. Visit 3, Day 6

The following activities and assessments will be performed:

- Blood pressure, pulse rate and body temperature will be monitored
- Safety laboratory tests (Table 5) will be collected
- Samples for DSA, PK and PD will be collected
- Urine sample for measurement of albumin/creatinine ratio

6.1.4. Visit 4, Day 8

The following activities and assessments will be performed:

- Blood pressure, pulse rate and body temperature will be monitored
- Safety laboratory tests (Table 5) will be collected
- Urine sample for measurement of albumin/creatinine ratio
- Samples for DSA, PK, PD and ADA (IgG) will be collected

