Currently used therapies include high dose IVIg +/- rituximab, Plasma Exchange (PE) with low dose IVIg +/- rituximab, eculizumab and a minimal experience with bortezomib. However, no therapy is currently approved, and patients are often treated with combination therapies that make analysis of efficacy of any one agent difficult. Thus, there is a large unmet clinical need for new therapies to prevent and treat AMR.

This study is designed to investigate the safety and efficacy of imlifidase removing anti-HLA antibodies in the treatment of active or chronic active AMR after transplantation. The primary objective of this study is to determine if imlifidase is effective in removing DSAs and thus lessen antibody mediated kidney damage in subjects experiencing post-transplant antibody mediated rejection.

Objectives

The primary objective of this study is to:

- Investigate the efficacy of imlifidase compared with PE in removal of DSA in patients who are experiencing an active or chronic active AMR episode after kidney transplantation

Secondary objectives of this study are to:

- Evaluate DSA levels up to 180 days after treatment
- Evaluate HLA-antibodies levels up to 180 days after treatment
- Evaluate the overall kidney function up to 180 days after treatment
- Investigate the occurrence of AMR up to 180 days after treatment
- Investigate the safety and tolerability of imlifidase compared to PE in patients experiencing active or chronic active AMR episodes
- Evaluate the number of PE-sessions needed
- Evaluate the pharmacokinetics, pharmacodynamics and immunogenicity of imlifidase

Endpoints

The primary endpoint of this study is:

- Maximum reduction in mean DSA level at any time point during the 5 days following the start of treatment

Secondary endpoints of this study are:

- DSA levels up to 180 days after treatment
- HLA-antibodies levels up to 180 days after treatment
- Kidney function change from baseline, (at screening), as evaluated by eGFR, P-creatinine and albumin/creatinine ratio in urine up to 180 days after treatment
- Proportion of subjects with graft loss within 180 days of treatment
- Signs of transplant glomerulopathy 180 days post treatment
- Change from baseline (at screening) in histopathology per Banff Criteria at 29 and 180 days

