12.3. Statistical Analysis of Endpoints

12.3.1. Primary efficacy endpoint

The primary endpoint is the maximum reduction in DSA (MFI sum for relevant DSAs) at any time point during the 5 days following the start of treatment. A subject will have at least one DSA and a DSA is considered relevant if it is at least 1000 MFI pre-dose. The reduction is derived as follows:

- 1) Calculate the reduction (%) in sum of DSAs as $100 \times (DSA_0 - DSA_t) / DSA_0$ for each subject and time point. Only DSAs with a pre-dose MFI of 1000 or more will be included in the calculations
- 2) Find the time point with maximum reduction within 5 days for each subject
- 3) The maximum reduction per subject will give a single value as the primary endpoint for the subject

Where DSA_t is the analysis result in total MFI for relevant DSAs at time t.

Due to the exploratory nature of this study, no formal hypothesis will be tested. The difference in reduction between the two treatments will be presented with 95% CI. Each subject will be given equal weight in the calculation of the treatment difference irrespective of number of DSAs for the subjects.

A summary table showing the proportion of reduction of DSAs calculated per subject will also be presented.

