4.6 Efficacy

4.6.1 Primary efficacy analysis

The primary endpoint is the maximum reduction in DSA at any time point during 5 days following start of treatment. No formal statistical hypothesis will be tested for the primary endpoint. The FAS and PPS set will both be used for the primary endpoint. The primary endpoint will be calculated as part of the ADaM programming.

The DSAs are given as levels of mean fluorescence intensity (MFI) and genetic region of interest. These parameters are used to calculate the reduction in DSA for individual patients in the following steps:

- 1) Determine the DSAs having MFI levels larger than or equal to 1000 at baseline for the considered patient. Calculate DSA_0 as the sum of these MFI levels.
- 2) Calculate DSA_t for each patient as the sum of the MFI levels for the time point t , using the DSAs from step 1.
- 3) The reduction (%) is calculated as $100 \times (DSA_0 - DSA_t) / DSA_0$ for each patient and time point. In the formula DSA_t is the total MFI level at time t .
- 4) The time point with maximum reduction within 5 days is found and chosen for each patient.

- 5) The maximum reduction per patient is a single value as the primary endpoint for the patient.

The difference in reduction between the two treatments will be presented with 95% CI in a table. The confidence interval for the difference in the reduction is found by using an Analysis of variance (ANOVA) model with treatment as fixed effect.

The reduction of DSAs calculated per patient will also be presented in a summary table by treatment and visit and presented in a mean plot by treatment and time point. The maximum reduction per patient will be listed by patient.

If the normality assumption is violated, sensitivity analyses using transformations of the primary endpoint will be performed.

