4.8 Other endpoints

No other endpoints are included in the study.

5 Deviations from protocol analysis

The primary endpoint from the protocol was: “Maximum reduction in mean DSA level at any time point during the 5 days following the start of treatment.” This has been changed to: “Maximum reduction in DSA level at any time point during the 5 days following the start of treatment” to avoid a misinterpretation that it is a mean across patients.

The Western blot is not applied for detectable intact IgG. Instead, the scoring is done on the SDS-PAGE where the scores 0, 1, 2, 3 mean no detectable intact IgG. The Western blot does not generate any quantifiable data as SDS-PAGE does. Therefore, it is not applied in the analyses.

The difference in proportion between treatments and 95% CI are not done for detectable intact IgG. The treatment group (not including imlifidase) will only generate score 5. Therefore, no additional information will be gained by comparing the two groups.

The time for the endpoint “Presence of intact IgG on SDS-PAGE until start of IVIg treatment”, also referred to as “Detectable intact IgG on a Western blot” in protocol, is changed. Instead of over 180 days, the endpoint is considered between the start of treatment and start of administration of IVIg. This is changed because the high dose IVIg will lead to detectable intact IgG, i.e. no meaningful conclusions on remaining intact IgG can be drawn after the administration on IVIg.

PKS is updated to only include patients treated with imlifidase. Blood samples will still be taken as planned for central analysis for non-imlifidase patients, but no portion will be used for PK and ADA analysis, as this is not applicable for non-imlifidase patients.

IA has been added to the endpoint “Number of sessions with PE within 180 days” as it is used for the same purpose as PE.

6 Quality control

SDTM data sets will be generated by programs in SAS software by reading in lab data and export data from Trial Master and converting to SDTM formats following the SDTM specifications. The QC will include:

- Independent Code review
- CRF annotation review vs SDTM content
- Direct QC of input vs output in SDTM on a sample of data
- Apply the Pinnacle 21 validator for STDM and ADAM

This three-pronged approach has proven to give a high-quality level corresponding to the expected for SDTM data

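### As scheduled, the 96 h DSA sample follows the start of high-dose IVIg in the imlifidase arm but not in the PE arm, and the 5-day maximum counts it with no sensitivity analysis.

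*Protocol*

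**What the plan says.** **Endpoint.** Protocol 12.3.1 says "Find the time point with maximum reduction within 5 days for each subject" and SAP 4.6.1 step 4 repeats the rule: "The time point with maximum reduction within 5 days is found and chosen for each patient". Neither makes a sample's eligibility depend on IVIg. The difference between arms is estimated by ANOVA with treatment as the only term, with a 95% CI. The only sensitivity analysis in SAP 4.6.1 is a transformation if normality fails, and SAP 4.6.3 plans no additional analyses.

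**Sampling.** Protocol 6.1.2 takes DSA at 2, 6 and 24 h, and then: "Samples for DSA, PK and PD will be collected at 48, 72, and 96 hours". The next sample is on Day 6. In the PE arm, Protocol Tables 3 and 4 ask for DSA to be drawn before PE where applicable.

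**IVIg, imlifidase arm.** It is given on day 4, no sooner than 72 h after the infusion, and may be spread over two days (Protocol 5.3 and 6.1.2). The order of sample and IVIg is fixed at 72 h only: "The 72-hour sample must be taken prior to high dose IVIg is given in the imlifidase arm". A patient in this arm who needs PE receives IVIg after the last PE session instead (Protocol 5.3).

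**IVIg, PE arm.** Protocol 6.1 says "PE-arm: high dose IVIg will be given after the last session of PE", and Protocol 1.2 places it on the last day of PE. The course is 5 to 10 sessions. How often sessions are held is not stated.

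**The concern.** The primary objective is to compare imlifidase with PE in removing DSA. At 2 to 72 h the samples compare those two treatments, on the same background steroids. At 96 h, under the planned schedule, they compare imlifidase plus IVIg with PE before IVIg. Protocol 1.1 names IVIg among the treatments in use for AMR ("Currently used therapies include high dose IVIg +/- rituximab") and notes that combination treatment makes it hard to judge any one agent.

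The form of the endpoint matters. A mean over time points could move either way when the 96 h value is included. A maximum can only rise or stay the same. If IVIg lowered MFI by 96 h, the fall would be credited to imlifidase; if it raised MFI, the rise would be ignored. The primary table as planned could not separate the two treatments.

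**Working it through.** **Step 1: which samples follow IVIg.** Inputs are the sampling and IVIg rules above. Assumptions: PE sessions daily from Day 1, no PE course stopped early, and no imlifidase patient diverted to PE.

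| DSA sample | Imlifidase arm | PE arm |
|---|---|---|
| 2, 6, 24, 48 h | before IVIg | before IVIg |
| 72 h | before IVIg (required) | before IVIg, after 3 sessions |
| 96 h | after IVIg has started | before IVIg, after 4 sessions |
| Day 6 (about 120 h) | after IVIg has started | after IVIg only if the course was five daily sessions |

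If sessions are less frequent, IVIg in the PE arm comes later still. Up to 96 h the imlifidase arm has 5 samples before IVIg out of 6; the PE arm has 6 out of 6. Neither document says whether Day 6 lies within the 5 days. If it does, some PE patients also have one post-IVIg sample, while imlifidase patients have two. The asymmetry lessens but remains.

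**Step 2: the plan's own precision figure.** Protocol 12.4 gives SDs of 6% and 4% for IgG reduction, assumes similar variability under PE, and expects a 95% CI about 8 points wide with 20 + 10 patients.

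- Width = 2 × t(0.975, 28 df) × SD × √(1/20 + 1/10)
- SD 5 (midpoint): 7.93. SD 4: 6.35. SD 6: 9.52.

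The stated figure is reproduced. The half-width at SD 5 is 7.93 / 2 = 3.97 points.

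**Step 3: bound on the effect.** Added to the imlifidase mean = share of patients whose maximum moves to 96 h because of IVIg × their average gain. Protocol 12.4 reports earlier 5-day IgG reductions of 90% and 93%. If DSA reductions before IVIg average the same (an assumption), the mean gain cannot exceed 100 − 90 = 10 or 100 − 93 = 7 points.

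Shares and gains below are assumed; the documents give none.

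| Share | Gain (points) | Added to arm mean | Fraction of half-width |
|---|---|---|---|
| any | 0 | 0 | 0 |
| 10% | 5 | 0.5 | 0.13 |
| 25% | 2 | 0.5 | 0.13 |
| 50% | 5 | 2.5 | 0.63 |
| 100% | 5 | 5.0 | 1.26 |

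**Step 4: separating IVIg from the extra sample.** A sixth sample raises a maximum a little by chance alone, and the PE arm has that sample too. A simulation of the imlifidase arm assumed a flat profile averaging 90%, total SD 5, within-patient SD 1, 2 or 3, and a cap at 100%. The rise in the mean maximum from including 96 h was:

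| Assumed IVIg effect | SD 1 | SD 2 | SD 3 |
|---|---|---|---|
| 0 points | 0.10 | 0.20 | 0.29 |
| 2 points | 0.96 | 0.75 | 0.74 |
| 5 points | 3.50 | 2.52 | 2.00 |

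Subtracting the first row leaves 0.86, 0.55 and 0.45 points for a 2-point effect, and 3.40, 2.32 and 1.71 for a 5-point effect. The first row also shows what a comparison of 5 imlifidase samples with 6 PE samples would cost imlifidase by chance: about 0.1 to 0.3 points.

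**The case against.** - **No IVIg effect on MFI is documented.** The protocol lists IVIg as an AMR therapy but gives neither size nor speed of any effect on DSA MFI, and the concern needs one within about 24 h. This stands: the documents show that the contrast could be affected, not that it is.
- **Imlifidase acts early.** Protocol 1.1 says the IgG pool is cleaved within hours and stays very low for about a week, and five samples precede IVIg. Most or all maxima may come by 72 h. This stands, and makes a zero effect plausible.
- **The intact-IgG precedent does not carry over.** A reader might infer from SAP section 5 that the sponsor already regards samples after IVIg as uninterpretable, since it says "no meaningful conclusions on remaining intact IgG can be drawn after the administration on IVIg". The reason there is that IVIg supplies intact IgG, the very thing being measured. That is specific to intact IgG and says nothing about DSA, so this point does not rest on it.
- **Exposure at 96 h varies.** IVIg may be split over two days, so the 96 h sample may follow only part of the dose, and a patient needing PE gets IVIg later. Both limit the reach of the point.
- **The data are partly visible already.** Tables 14.2.3 and 14.2.4, Figure 15.1.1 and Listing 16.2.1.1 show DSA reduction by time point or patient, and SAP 4.5 tabulates IVIg timing. But none of these gives a between-arm interval for the per-patient maximum without post-IVIg samples.
- **A restricted maximum has its own tilt.** Pre-IVIg samples number 5 against 6 up to 96 h, which slightly disfavours imlifidase. A cut at 72 h drops the effect of later PE sessions. This stands as a reason to supplement the primary rule, not to replace it.

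What survives is the timing difference and the absence of any analysis that addresses it.

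**Conclusion.** The point holds in a limited form. Under the Step 1 assumptions, a post-IVIg sample at 96 h is eligible for the maximum in one arm only, and it can act in one direction only. The size is unknown. It is zero if all maxima occur by 72 h. It averages at most about 7 to 10 points if the earlier IgG reductions carry over to DSA. Between those limits it depends on an IVIg effect that the documents do not supply; an assumed 2-point effect gives under 1 point, against a CI half-width of about 4.

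Two stronger readings are tempting. One is that the primary estimate is biased towards imlifidase; without a documented IVIg effect on MFI within a day, that is not established. The other is that only the imlifidase arm receives IVIg; both arms do, and only the timing relative to the 96 h sample differs. For a descriptive study without hypothesis tests, this is a cheap improvement to the analysis and not a defect that invalidates the primary result.

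**What to change.** 1. Keep the planned primary interval as it is.
2. State in SAP 4.6.1 whether the Day 6 sample lies within the 5-day window.
3. Add beside the primary result a sensitivity estimate: the between-arm difference in maximum reduction with 95% CI, using in each arm only samples drawn before the start of high-dose IVIg.
4. Preferably also show the difference with both arms limited to samples up to 72 h, so that each has five.

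If the versions agree, the question is closed. If they differ, the reader sees how much of the contrast depends on post-IVIg samples.

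The cost is a short derivation and one or two table rows. Sample dates and times are already recorded (Protocol 7.1.1), and the time point of IVIg is already due to be tabulated (SAP 4.5). The drawback is lost information: the pre-IVIg version gives up the imlifidase 96 h sample, and the 72 h version also omits PE sessions after the third (if daily). Both should therefore supplement the primary result. No change to the IVIg schedule is implied.

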6.1.5. Visit 5, Day 11 (+/- 2 days)

The following activities and assessments will be performed:

- Blood pressure, pulse rate and body temperature will be monitored
- Safety laboratory tests (Table 5) will be collected
- Urine sample for measurement of albumin/creatinine ratio
- Samples for DSA, PK, PD and ADA (IgG) will be collected

Imlifidase arm: Rituximab will be given 5 days after the completion of the IVIg infusion

6.1.6. Visit 6, Day 15 (+/- 2 days)

The following activities and assessments will be performed:

- Blood pressure, pulse rate and body temperature will be monitored
- Safety laboratory tests (Table 5) will be collected
- Urine sample for measurement of albumin/creatinine ratio
- Samples for DSA, PK, PD and ADA (IgG) will be collected

6.1.7. Visit 7, Day 22 (+/- 3 days)

The following activities and assessments will be performed:

- Blood pressure, pulse rate and body temperature will be monitored
- Safety laboratory tests (Table 5) will be collected

- Urine sample for measurement of albumin/creatinine ratio
- Samples for DSA, PD and ADA (IgG) will be collected

6.1.8. Visit 8, day 29 (+/- 3 days)

The following activities and assessments will be performed:

- Blood pressure, pulse rate and body temperature will be monitored
- Safety laboratory tests (Table 5) will be collected
- Urine sample for measurement of albumin/creatinine ratio
- Kidney biopsy will be performed
- Samples for DSA, PD and ADA (IgG) will be collected
- Austria only, pregnancy test (serum)

6.1.9. Visit 9, Day 64 (+/- 7 days) and Visit 10, Day 90 (+/- 7 days)

The following activities and assessments will be performed:

- Blood pressure, pulse rate and body temperature will be monitored
- Safety laboratory tests (Table 5) will be collected
- Urine sample for measurement of albumin/creatinine ratio
- Samples for DSA, PD and ADA (IgG) will be collected
- Austria only, pregnancy test (serum)

6.1.10. Visit 11 (follow up, end of study), day 180 (+/- 14 days)

The following activities and assessments will be performed:

- Physical examination
- Blood pressure, pulse rate and body temperature will be monitored
- Safety laboratory tests (Table 5) will be collected
- ECG
- Pregnancy test (serum)
- Urine sample for measurement of albumin/creatinine ratio
- Kidney biopsy will be performed
- Samples for DSA, PD and ADA (IgG) will be collected

6.2. Flow Chart imlifidase arm

Table 1: Study flow chart imlifidase arm, Screening to End of Study

Visit Number	1	2	3	4	5	6	7	8	9	10	11	
Type of visit	Screening	Treat- ment	Assessments								FU/End of study	
Day		1-5	6	8	11	15	22	29	64	90	180	
Assessment /Time window			0	0	±2d	±2d	±3d	±3d	±7d	±7d	±14d	
Informed Consent	X	See table 2										
Demographics	X											
Medical/surgical history, incl transplantation and previous AMRs	X											
Record historical creatinine values	X											
Record number of pregnancies (if applicable)	X											
Inclusion/exclusion criteria	X											
Randomization	X											
Physical examination	X											X
Height and weight	X											
Blood pressure and pulse rate	X			X	X	X	X	X	X	X	X	X
Respiratory frequency	X											
Body temperature	X			X	X	X	X	X	X	X	X	X
PCR test for SARS-CoV-2 virus	X											
ECG	X											X
Pregnancy test (serum)	X											X
Pregnancy test (serum) Austria	X								X	X	X	X
Safety laboratory tests (incl creatinine for eGFR)	X			X	X	X	X	X	X	X	X	X
Urine sample for measurement of albumin/creatinine ratio	X			X	X	X	X	X	X	X	X	X
ADA (IgE)	X ^a											
DSA, incl HLA antibodies and functionality	X ^b			X	X	X	X	X	X	X	X	X
PK sampling			X	X	X	X						

Table 1: Study flow chart imlifidase arm, Screening to End of Study

Visit Number	1	2	3	4	5	6	7	8	9	10	11	
Type of visit	Screening	Treat- ment	Assessments								FU/End of study	
Day		1-5	6	8	11	15	22	29	64	90	180	
Assessment /Time window			0	0	±2d	±2d	±3d	±3d	±7d	±7d	±14d	
PD sampling			X	X	X	X	X	X	X	X	X	
ADA(IgG)				X	X	X	X	X	X	X	X	
Kidney biopsy	X ^c								X ^c			X ^c
Methylprednisolone /Prednisolone			Will be given according to treatment schedule (section 5.3) and continue as long as prescribed by investigator									
Antibiotic prophylaxis			Treatment will continue until IgG levels return to acceptable values, as judged by the investigator									
Rituximab						X ^d						
Concomitant medication and other treatment	Throughout the study											
Adverse events	Throughout the study											

- ^{a)} Sample will be taken pre-dose but no need to wait for result before start of treatment
- ^{b)} One DSA sample will be sent to local lab for evaluation for inclusion and one DSA sample will be collected for analysis at Hansa Biopharma
- ^{c)} One piece of tissue will be sent to local pathology lab and one piece of tissue will be sent for analysis at [REDACTED]. If kidney biopsy is performed prior to screening, a piece of tissue cannot be sent for [REDACTED] unless site stores tissue in mRNA later as standard of care. Then the tissue may be sent for [REDACTED] analysis after informed consent is signed.
- ^{d)} Rituximab will be given 5 days after completed high dose of IVIg

Table 2: Study flow chart imlifidase arm, visit 2, treatment

Visit Number	2									
Time	Pre-dose	Treat-ment	30 min	1 h	2 h	6 h	24 h	48 h	72 h	96 h
Assessment /Time window			±10 min	±10 min	±15 min	±30 min	±2h	±2h	±6h	±6h
Blood pressure and pulse rate	X				X	X	X	X	X	X
Respiratory frequency	X						X	X	X	X
Body temperature	X						X	X	X	X
Safety laboratory tests (incl creatinine)							X	X	X	X
Methylprednisolone/prednisolone ^a	X						X	X	X	X
Antihistamine	X									
Antibiotic prophylaxis	X		Treatment will continue until IgG levels return to acceptable values, as judged by the investigator							
DSA, incl HLA antibodies and functionality	X				X	X	X	X	X ^b	X
PK sampling	X		X	X	X	X	X	X	X ^b	X
PD sampling	X				X	X	X	X	X ^b	X
ADA (IgG)	X						X			
P-creatinine (for calculation of eGFR)	X									
Urine sample for measurement of albumin/creatinine ratio	X						X	X	X	X
Imlifidase infusion		X								
High dose IVIg									X ^c	
Concomitant medication and other treatment	Throughout the visit									
Adverse events	Throughout the visit									

^{a)} Methylprednisolone/prednisolone will be given according to the treatment schedule in section 5.3

^{b)} Samples should be taken prior to start of high dose IVIg is given

^{c)} May be given over two days

